6.1 Enrolment

Potential participants will be recruited via different organisations and platforms (including, but not limited to):

- Eczema charities: e.g. National Eczema Society (http://www.eczema.org/),
 Eczema Outreach Support (https://www.eos.org.uk/), Nottingham Support Group for Carers of Children with Eczema (http://www.nottinghameczema.org.uk/index.aspx).
- School of Medicine / Centre of Evidence Based Dermatology communication channels (e.g. Twitter, website, existing mailing lists and newsletters).

Trial	Eczema Monitoring Online (EMO)	Protocol		Date:	08-04-2021	Page:	12 of 25
name:	Trial Protocol	version:	1.0				

- Call for Participants website (https://www.callforparticipants.com). An open platform that brings together researchers to promote their studies and potential participants interested in taking part in studies.
- **Social media:** the study will be advertised on a range of platforms e.g. Facebook, Twitter, Instagram.
- Other organisations/online platforms/ individuals e.g. resharing via social media.

Recruitment is expected to start in June 2021 and it is anticipated to last for approximately 9 months. Participant retention and completion of follow-up assessments will be promoted by using various methods (including, but not limited to): email reminders, text reminders, telephone calls. Newsletters and other appropriate communications may be used to aid retention. Upon completion of the follow up questionnaires at 8 weeks, participants will be able to enter an optional price draw for a chance to win one of six £20 vouchers to say thank you for taking part. The recruitment strategy will focus on the UK, as participation is online so it will not be restricted by geography.

6.2 Randomisation

Participants will complete the consent form followed by baseline characteristics and eligibility screening. All assessments and questionnaires will be developed by using the Research Electronic Data Capture (REDCap) software. Those who do not fulfil the eligibility criteria of a POEM score of 3 or above will be provided with information explaining that they were not eligible to take part in the study and will be signposted to other online resources.

Eligible participants will be randomised online to either the intervention group or to the control group, using the REDCap software. The randomisation schedule will be based on computer generated random codes, using random permuted blocks of randomly varying size, stratified by age and baseline disease severity.

6.3 Blinding

This is a methodological trial and there will be no treatment intervention involved.

The nature and the objectives of this study does not allow complete transparency towards participants about the purpose of this trial. If they knew the aim of the trial, it would likely influence their behaviour, which would completely undermine the trial objectives. Therefore, potential participants will be told that the aim is to evaluate how eczema changes over time. It appears to be an appropriate approach as this is a non-treatment intervention trial and participants will not be at disadvantage or risk because of taking part. After randomisation, participants will be informed about how often they will be asked to complete the questionnaires. The PhD student will deal with participant queries, thus she will have access to group allocation, but the other trial team members and the trial statistician will remain blinded.

Trial	Eczema Monitoring Online (EMO)	Protocol		Date:	08-04-2021	Page:	13 of 25
name:	Trial Protocol	version:	1.0				

7. Trial Intervention

7.1 Intervention

The trial intervention will be the POEM questionnaire. Only the intervention group will receive the POEM questionnaire (intervention) each week. This will allow participants to monitor their symptoms regularly.

Both groups, the intervention group and the control group will receive POEM at baseline and 8 weeks, as part of the primary outcome assessment, which will enable us to evaluate whether regular symptom monitoring affects eczema severity.

8. Trial Procedures and Assessments

8.1 Summary of Assessment

Table 1. Summary of Trial Assessments.

ASSESSMENTS	Week 0	From Week 1 to Week 7	Week 8
Baseline characteristics	✓		
Eligibility Screening	✓		
Informed Consent	✓		
Randomisation	✓		
Online Weekly POEM			
(Intervention Group)			
No intervention			
(Control Group)			
Disease severity (POEM)	✓		✓
Eczema control (RECAP)	√		✓
Itch intensity measure (NRS Itch)	√		✓
Treatment use Question	√		√
Patient Global Assessment (PGA)	✓		✓
Global bother Question	✓		✓

I	Trial	Eczema Monitoring Online (EMO)	Protocol		Date:	08-04-2021	Page:	14 of 25
	name:	Trial Protocol	version:	1.0				

8.2 Schedule of Assessments

Enrolment (Week 0):

- Participant Information Sheet (PIS): interested individuals will be provided with a link to the study website that will take them to the PIS, which will include the summary of research aims, intervention and information about data handling. Upon reading it, they can proceed to the consent form.
- Informed consent: potential participants will be required to read, complete and submit the consent form, if they would like to take part in the study.
- Baseline characteristics: age, gender, ethnicity, country, postcode (UK only), self-report or parent/carer report of doctor's eczema diagnosis and what eczema treatment is currently used.
- Eligibility screening: eczema severity assessed by the POEM questionnaire.
- Randomisation: upon completion of the eligibility screening, eligible participants will be randomised online to either the intervention group or to the control group, using the REDCap software.

Baseline (Week 0):

The following online questionnaires will be completed by both study groups at baseline:

- POEM
- RECAP
- NRS Itch
- Patient Global Assessment (PGA)
- Bother question
- Treatment use question

Post randomisation (from Week 1 to Week 7): the intervention group will be sent weekly POEM questionnaires for completion. The control group will not receive questionnaires during this time-frame.

Follow-up (Week 8):

Both study groups will be sent the following questionnaires at week 8:

POEM

Tr	rial	Eczema Monitoring Online (EMO)	Protocol		Date:	08-04-2021	Page:	15 of 25
na	ame:	Trial Protocol	version:	1.0				

- RECAP
- NRS ltch
- PGA
- Bother question
- Treatment use question

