13.2 Definition of Outcome Measures

13.2.1 Primary outcome measure

 Eczema severity: change in eczema severity from baseline to 8 weeks assessed by the POEM score.

13.2.2 Secondary outcome measures:

- Adherence to standard treatment use: will be assessed in two ways:
 - Change in eczema treatment use from baseline to 8 weeks assessed by emollient and topical corticosteroid use over the last week.
 - Change in eczema treatment use from baseline to 8 weeks assessed by overall eczema treatment use over the last two months.
- Missing data: the proportion of fully completed questionnaires at 8 weeks.

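### The treatment-use items that anchor both adherence outcomes are scheduled after randomisation, and the protocol does not say which of two Week 0 POEMs is the baseline

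*Protocol*

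**What the plan says.** Section 6.2 gives the order up to randomisation: "Participants will complete the consent form followed by baseline characteristics and eligibility screening". Randomisation follows, "using random permuted blocks of randomly varying size, stratified by age and baseline disease severity".

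Section 8.2 agrees. Its Enrolment block holds the screening step ("Eligibility screening: eczema severity assessed by the POEM questionnaire") and then randomisation: "upon completion of the eligibility screening, eligible participants will be randomised online to either the intervention group or to the control group". A separate Baseline (Week 0) block comes next: "The following online questionnaires will be completed by both study groups at baseline". That block lists POEM, RECAP, NRS itch, PGA, the bother question and the treatment-use question.

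On disclosure, section 6.3 says: "After randomisation, participants will be informed about how often they will be asked to complete the questionnaires".

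Two sets of outcomes use a baseline value. The primary outcome (13.2.1) is "change in eczema severity from baseline to 8 weeks assessed by the POEM score". The first adherence outcome (13.2.2) is "Change in eczema treatment use from baseline to 8 weeks assessed by emollient and topical corticosteroid use over the last week"; the second is the same kind of change, for overall treatment use with a two-month recall. Section 13.3 adjusts the primary regression for the stratification variables and for other variables that look imbalanced at baseline.

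**The concern.** A reference value for change should be fixed before the arms exist. Here the treatment-use items come after randomisation, and nothing delays disclosure of the questionnaire schedule until they are answered. Participants are not blind to how often they will be asked, and the items are self-reported or proxy-reported. A difference between arms in how these items are answered would enter the estimated effect on adherence, which is the trial's second objective and its proposed mechanism. People randomised who never complete the set drop out of both adherence comparisons, and that loss need not be equal between arms.

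For POEM the difficulty is ambiguity. It is listed in two Week 0 blocks, and the protocol does not say which one is the baseline for the change score. The rule on adjusting for apparent imbalance has the same gap: as written, it could bring variables measured after randomisation into the primary model.

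**Working it through.** **1. Which Week 0 items precede randomisation (sections 6.2 and 8.2)**

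| Item | Before randomisation | Listed after randomisation | Used for |
|---|---|---|---|
| Demographics, treatment currently used | yes | no | description; age for stratification |
| POEM | yes (screening) | yes (baseline block) | eligibility, stratification, primary change |
| Three treatment-use items | no | yes | both adherence outcomes |
| RECAP, NRS itch, PGA, bother | no | yes | validation work (8.3) |

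Stratifying by baseline severity needs a severity value before allocation. The screening POEM is the only one described. The three treatment-use items have no such counterpart: the pre-randomisation question on current treatment is not described as the same three items.

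**2. How a baseline shift would act**

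Let τ be the true effect on the week 8 value, and s the difference between arms in baseline reporting caused by allocation.

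- Change from the affected baseline, without adjustment for it: the estimate is τ − s.
- Adjustment for the affected baseline, with slope b: the estimate is τ − b·s.
- Week 8 value adjusted only for a pre-randomisation baseline: the estimate is τ.

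For treatment use, only the first two cases are available, because no earlier value of those items is collected. The protocol gives no scale, SD or target difference for them, so the bias cannot be expressed in outcome units.

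**3. POEM, worst case only**

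This applies only if a second, post-randomisation POEM is the baseline.

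- Inputs from 13.1: difference 2.5, SD 6.5, 80% power, 106 per group. The two-sided level has no number in the text, so 5% is assumed.
- Plan's figure: n per group = 2 × (1.960 + 0.842)² × 6.5² / 2.5² ≈ 106.1, which agrees with the stated 106 to rounding. Then 106 / 0.8 = 132.5, rounded up to 133, or 266 in total. The sample size reproduces and is not affected by this point.
- Standard error = 6.5 × √(2/106) ≈ 0.89, taking 6.5 as the SD of the analysed quantity.

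The documents give no value for s, so it is assumed across a range:

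| Assumed s (points) | Share of 2.5 | True error of a nominal 5% test | Power if the bias opposes a 2.5 effect |
|---|---|---|---|
| 0.25 | 10% | 5.9% | 71% |
| 0.5 | 20% | 8.7% | 61% |
| 1.0 | 40% | 20% | 39% |

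These figures are for the unadjusted change score. With an assumed slope of 0.3 to 0.7 on the affected baseline, a 0.5-point shift leaves a bias of 0.15 to 0.35 points and a true error of 5.3% to 6.8%. With the screening POEM as baseline, the bias by this route is zero.

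**4. Missing treatment-use baseline**

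If 5% of those randomised (assumed) do not complete the set: 0.05 × 266 = 13.3, about 13 people. Half or double that rate gives 6.65 or 26.6, about 7 or 27.

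**The case against.** The strongest reply is that the order is less firm than it looks and that the primary outcome is largely safe.

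- The participant-flow figure is not available in the text reviewed. The post-randomisation heading in 8.2 is attached to Weeks 1 to 7, and a phrase about both groups need not fix timing. Table 1 does not settle the order either: it lists consent after eligibility screening, so its rows are not chronological. This lowers certainty. Even so, 6.2 and 8.2 both run from screening to randomisation, and no visible text puts the baseline set earlier.
- A reader might infer that the primary effect is biased point for point. The documents do not support that. The severity variable used for stratification, and named for adjustment in 13.3, must predate allocation. Table 1 has a single Week 0 entry for POEM as a severity measure, which fits one POEM serving both purposes.
- A reader might also infer that the trial's own hypothesis predicts biased reporting. It does not: the stated mechanism is behaviour change. No weekly POEM has been sent at Week 0, the treatment-use items look back in time, and participants are not told the true aim. If everything is done in one sitting, only a shift in reporting remains, and it may be small.
- RECAP, NRS itch, PGA and bother are not trial outcomes, so their timing threatens no planned comparison unless the imbalance rule brings them into the model.
- The planned 20% allowance for loss exceeds the illustrative 5%, so numbers alone are not the problem.

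All of this stands, and it narrows the point. It does not supply a pre-randomisation value of the three treatment-use items.

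**Conclusion.** The point holds in a limited form. As written, both adherence outcomes measure change from a value self-reported after randomisation and possibly with allocation known, and people who stop in between have no such value. The protocol also leaves open which POEM is the baseline for the primary change score.

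The size of any bias is unknown. The POEM table above is a worst case on assumed shifts and applies only if a second, post-randomisation POEM is used; it is not an estimate of bias in the primary result. The count of 13 also rests on an assumed rate, and nothing in the protocol indicates that the loss would differ by arm.

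A statistical analysis plan could name the screening POEM as the baseline, but it cannot create treatment-use values that were not collected before randomisation. The order of collection therefore belongs in the protocol. This should be fixed; the documents do not show that the trial's main conclusion is at risk.

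**What to change.** 1. In 6.2 and 8.2, place the treatment-use items before randomisation and before the questionnaire schedule is shown. The other baseline questionnaires can move with them at no extra cost.
2. Name the pre-randomisation screening POEM as the single baseline POEM for stratification, change and adjustment, and do not repeat it at Week 0.
3. In 13.3, limit any adjustment for baseline imbalance to variables measured before randomisation.

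The cost is a reordered REDCap workflow and a few lines of protocol text. A longer sequence before randomisation may lose a few people at that stage. That costs some recruitment, whereas the same losses after randomisation would affect comparability of the arms.

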8.3 Trial Assessments

The only questionnaire that will be used to assess the primary outcome in this study is POFM

- Patient-Oriented Eczema Measure (POEM) (16): a well-validated, reliable and simple tool that demonstrates good responsiveness to change and used for monitoring eczema severity in both children and adults. It is a seven item questionnaire that assesses self-reported or proxy reported symptoms over the last week, including: frequency of itch, sleep loss, bleeding, wheeping/oozing, cracking, flaking and dryness. It provides a score from 0 to 28, with higher score representing more severe eczema. Missing data will be handled in accordance with the instrument developer's recommendations.
- Treatment use Question: this will include three single item questions that will be asked
 at baseline and at week 8 to assess adherence to emollient and topical steroid use over
 the last week and also assess overall eczema treatment use over the last 2 months.

The following questionnaires are included in this study to be able to undertake validation studies based on this trial's dataset.

- NRS Itch (18): Peak Pruritus Numerical Rating Scale (NRS) a validated, reliable, widely-used measure that assesses the intensity of peak (worst) pruritus (itch) during the past 24 hours. It provides a score from 0 to 10, higher score means more intense itch.
- Recap of Atopic Eczema (RECAP) (19): a validated, seven item questionnaire that
 captures self-reported or proxy reported eczema control. It is a recently developed
 instrument and further validation studies are required to investigate how it performs in
 trials. The assessment of the minimal clinically important difference (MCID) study, a
 severity banding study or other needed validation studies will be conducted based on
 this trial's dataset, which will improve the interpretability of RECAP in eczema research.
- Patient's Global Assessment (PGA): single item global assessment of eczema. It is a
 six point Likert scale (clear, almost clear, mild, moderate, severe, very severe), used to
 gauge an overall sense of current disease severity. This might be used as an anchor in
 one of the validation studies.

Trial	Eczema Monitoring Online (EMO)	Protocol		Date:	08-04-2021	Page:	16 of 25
name:	Trial Protocol	version:	1.0				

Bother Question: It is a global assessment of eczema in the preceding week to gain an
insight into overall disease severity. This might be used as an anchor for the validation
studies.

8.4 Withdrawal Procedures

Participants will be free to withdraw from the trial anytime, without having to give a reason. Participants will be informed that this will not have any negative consequences on them. The PIS and the consent form will make participants aware that should they withdraw from the trial, the data collected to date cannot be erased and may be still used and included in the analysis.

9. Adverse Event Reporting

This is a non-treatment intervention trial and the occurrence of an adverse event as a result of participation in this study is not expected and no adverse event data will be collected. The researchers will be unable to provide medical advice. Thus, if medical concerns arise the researchers will suggest participants contact their general practitioner or relevant healthcare professional to discuss their concerns. This information will be always provided in the form of written information at the end of the questionnaire completion.

10. Data Handling

10.1 Case Report Form

Traditional case report forms (CRFs) will not be used as such because data collection will be via online, patient-reported or proxy reported questionnaires as described in section 8. Each participant will be assigned a study identity code number for use on the electronic database. The study database and electronic documents will be treated as confidential and held securely in accordance with regulations.

10.2 Source Data

Source documents will include consent forms and all the online questionnaires used in this study. Only study staff shall have access to study documentation other than the regulatory requirements listed below. All source documents shall be made available at all times for review by the Chief Investigator (CI) and inspection by relevant regulatory authorities.

10.3 Data Management

Data will be handled in accordance with the study Data Management Plan.

I	Trial	Eczema Monitoring Online (EMO)	Protocol		Date:	08-04-2021	Page:	17 of 25
	name:	Trial Protocol	version:	1.0				

11. Quality Control and Quality Assurance

11.1 Study Conduct

Study conduct may be subject to systems audit for inclusion of essential documents; permissions to conduct the study; CVs of study staff and training received; local document control procedures; consent procedures and recruitment logs; adherence to procedures defined in the trial protocol (e.g. inclusion / exclusion criteria).

11.2 Study Data

Monitoring of study data shall include confirmation of informed consent; source data verification; data storage procedures; local quality control checks and procedures, back-up and disaster recovery of any local databases. The CI or delegate (PhD student) shall carry out monitoring of study data as an ongoing activity. Study data and evidence of monitoring and systems audits will be made available for inspection by the REC as required.

11.3 Record Retention and Archiving

In compliance with the ICH/GCP guidelines, regulations and in accordance with the University of Nottingham Code of Research Conduct and Research Ethics, the CI will maintain all records and documents regarding the conduct of the study. These will be retained for at least 7 years or for longer, if required. If the responsible investigator is no longer able to maintain the study records, a second person will be nominated to take over this responsibility.

11.4 Statement of Confidentiality

Individual participant medical or personal information obtained as a result of this study are considered confidential and disclosure to third parties is prohibited with the exceptions noted above. Participant confidentiality will be further ensured by utilising identification code numbers.

If information is disclosed during the study that could pose a risk of harm to the participant or others, the researcher will discuss this with the CI and where appropriate report accordingly. Data generated as a result of this study will be available for inspection on request by the University of Nottingham representatives, the REC and the regulatory authorities.

12. End of Trial Definition

The end of trial is defined in this study as once database has been locked and primary analyses conducted. The PhD student will notify the University of Nottingham's REC when the trial has ended, and a summary of the study report will be provided within 12 months of the end of trial.

Trial	Eczema Monitoring Online (EMO)	Protocol		Date:	08-04-2021	Page:	18 of 25
name:	Trial Protocol	version:	1.0				

13. Statistical Considerations

13.1 Sample Size Calculation

Assuming a standard deviation of 6.5, the estimated sample size to detect a between group difference of 2.5 in eczema severity score with 80% power and with a two-sided significance level is a total of 212 participants (106 per group). Allowing for 20% loss to follow up, the required total sample size for this trial is 266 participants (133 per group). These statistical assumptions are in line with the Eczema Care Online (ECO) trial (20), which is also an online trial that included a similar disease severity population to our study.

13.2 Definition of Outcome Measures

13.2.1 Primary outcome measure

 Eczema severity: change in eczema severity from baseline to 8 weeks assessed by the POEM score.

13.2.2 Secondary outcome measures:

- Adherence to standard treatment use: will be assessed in two ways:
 - Change in eczema treatment use from baseline to 8 weeks assessed by emollient and topical corticosteroid use over the last week.
 - Change in eczema treatment use from baseline to 8 weeks assessed by overall eczema treatment use over the last two months.
- Missing data: the proportion of fully completed questionnaires at 8 weeks.

